## **6.3. Baseline and Other Summaries and Analyses**

### **6.3.1. Study Conduct: Subject Disposition, Vaccine Administration, Blood Samples, and Screen Failures**

The numbers and percentages of subjects who are randomized will be included in the subject disposition summary: screening, open-label vaccine administration, and follow-up will be summarized. The reasons for withdrawal will also be tabulated. The reasons for withdrawal will be those specified in the database; no rewording/recoding will be done.

Subjects excluded from the evaluable immunogenicity population will also be summarized with reasons for exclusion.

The numbers and percentages of subjects randomized, vaccinated, and providing blood samples within the prespecified time frame, as well as before and after the specified time frame, will be tabulated for each vaccine group and for the total.

A listing of noncompliant vaccine administration will be provided. The protocol deviations will be listed. Subjects who do not receive the vaccine as randomized will be listed. A listing of subjects who withdrew because of AEs will be provided.

All randomized subjects will be used to generate these tables. All of the summary tables will be presented for each vaccine group and for the total.

Subjects who sign the informed consent document but are screen failures will be also summarized separately for each vaccine group.

### **6.3.2. Demographic, Medical History, and Baseline Characteristics**

Descriptive summary reports for demographic characteristics will be provided for each vaccine group for the evaluable immunogenicity (infant and toddler), all-available immunogenicity (infant and toddler), and safety (infant and toddler) populations.

Descriptive summary reports for medical history will be provided for each vaccine group for the infant safety population only.

### **6.3.3. E-Diary Completion**

Variables defined in [Section 3.5.2](#) will be summarized with descriptive statistics for each vaccine group and for the total (ie, MDV and PFS combined) after each dose in the infant series and after the toddler dose. The respective safety populations will be used.

### **6.3.4. Analyses of Missing Immunogenicity Values**

For each serotype, the number of subjects with missing values at each blood sampling point will be provided. Missing antibody concentrations and IgG concentrations will be compiled separately.

## **6.4. Other Safety Summaries and Analyses**

All safety analyses will be summarized based on the safety populations in accordance with Pfizer reporting standards.

#### **6.4.1. Adverse Events**

It should be recognized that most studies are not designed to reliably demonstrate a causal relationship between the use of a pharmaceutical product and an AE or a group of AEs. Except for select events in unique situations, studies do not employ formal adjudication procedures for the purpose of event classification. As such, safety analysis is generally considered as an exploratory analysis and its purpose is to generate hypotheses for further investigation. The 3-tier approach facilitates this exploratory analysis.

The 3-tier approach is discussed in [Section 3.5.1](#). The statistical methodology is described in [Section 5.2.1](#).

Besides the primary safety endpoints described in [Section 3.1](#), incidences of SAEs will also be compiled for the intervals from the first vaccination up to 1 month after the infant series, from 1 month after the infant series up to the toddler dose, and from the toddler dose up to 1 month after the toddler dose. The first 2 intervals will be analyzed using the infant safety population. The third interval, from the toddler dose up to 1 month after the toddler dose, will be analyzed using the toddler safety population.

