9.4. Safety Analysis

Local injection site reactions, systemic events, and AEs will be summarized by vaccine group and by vaccination.

The proportions of subjects with local reactions at the injection site and systemic events reported on any day within the 7-day period after each vaccination will be estimated for each vaccine group. Local reactions will not be compiled for concurrent vaccinations.

Local reactions and systemic events that persist beyond Day 7 will be listed in the CSR.

AEs will be categorized according to the Medical Dictionary for Regulatory Activities (MedDRA). AEs within 1 month after vaccination will be summarized by vaccine group for each vaccination separately. AEs will also be summarized from the first dose up to 1 month after the infant series.

SAEs will be summarized from the first dose up to 1 month after the toddler dose.

Newly diagnosed chronic medical conditions will be summarized from 1 month after the infant series up to the toddler dose.

All safety analyses will be performed on the safety population, which will include any subject with at least 1 vaccination. Subjects will be assigned to the vaccine actually received. If a subject receives different vaccines at different time points, then local reactions, systemic events, and AEs immediately following the vaccination will be assigned to the vaccine most recently received. Compilation of AEs or SAEs from the first infant dose up to the toddler dose will be assigned to the vaccine received. If a subject receives both vaccines during the infant series, then the subject will be assigned to the randomized vaccine group.

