### 3. ENDPOINTS AND BASELINE VARIABLES: DEFINITIONS AND CONVENTIONS

#### 3.1. Primary Endpoints

- Incidence of local reactions and systemic events at the following time periods in the MDV group and in the PFS group:
  - Within the 7 days after the first dose of the infant series.
  - Within the 7 days after the second dose of the infant series.
  - Within the 7 days after the third dose of the infant series.
  - Within the 7 days after the toddler dose.
- Incidence of adverse events (AEs) in the MDV group and in the PFS group from the first dose up to 1 month after the infant series.
- Incidence of AEs in the MDV group and in the PFS group from the toddler dose up to 1 month after the toddler dose.
- Incidence of serious adverse events (SAEs) in the MDV group and in the PFS group from the first dose up to 1 month after the toddler dose.
- Incidence of newly diagnosed chronic medical conditions in the MDV group and in the PFS group from 1 month after the infant series up to the toddler dose.

Each day of vaccination will be considered Day 1.

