#### **4.3. Safety Analysis Populations**

Separate safety populations will be defined for the infant series and the toddler dose. Each safety population will include all subjects who receive at least 1 dose of the investigational product for the indicated regimen. In each population subjects will be assigned to the vaccine actually received. If a subject receives different vaccines at different time points, then local reactions, systemic events, and AEs immediately following the vaccination will be assigned to the vaccine most recently received. Compilation of AEs or SAEs from the first infant dose up to the toddler dose will be assigned to the vaccine received. However, subjects who receive both vaccines during the infant series will be assigned to their randomized vaccine group for this compilation of AEs or SAEs.

Subjects who lack any safety data for a particular vaccination will be excluded from analysis.

Subjects vaccinated but not randomized will be included in the safety population for safety analysis. The results from these subjects will be reported under the group corresponding to the vaccine they actually received.

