## 6. ANALYSES AND SUMMARIES

### 6.1. Primary Endpoint(s)

**Endpoints:** Safety endpoints in [Section 3.1](#).

- Analysis intervals:

Endpoints for local reactions and systemic events: 7 days after each dose of the infant series and the toddler dose.

Endpoints for AEs: from the first dose up to 1 month after the infant series. Also from the toddler dose up to 1 month after the toddler dose.

Endpoints for SAEs: from the first dose up to 1 month after the toddler dose.

Endpoint for newly diagnosed chronic medical conditions: from 1 month after the infant series up to the toddler dose.

- Analysis population: Infant or toddler safety population, as relevant. SAE analysis will include subjects in either the infant or toddler safety population.
- Analysis methodology: Descriptive.
- Supporting objective: Primary objective.

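### SAE incidence between the post-infant-series visit and the toddler dose is divided by every infant ever dosed, and no denominator is named for newly diagnosed chronic conditions over the same interval

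*SAP*

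**What the plan says.** SAP 6.4.1 splits SAEs into three intervals: the infant series plus one month, the gap from then to the toddler dose, and the month after the toddler dose. On the population it states: "The first 2 intervals will be analyzed using the infant safety population". The third interval uses the toddler safety population.

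SAP 4.3 defines these sets: "Each safety population will include all subjects who receive at least 1 dose of the investigational product for the indicated regimen". Protocol 9.4 is equally broad: "All safety analyses will be performed on the safety population, which will include any subject with at least 1 vaccination". SAP 4.4 defines no further population.

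SAP 3.1 lists newly diagnosed chronic medical conditions as a primary endpoint over the same gap, "from 1 month after the infant series up to the toddler dose". For the population, SAP 6.1 says only "Infant or toddler safety population, as relevant". It then specifies the set for SAEs but not for chronic conditions.

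The one exclusion that might bear on this is in SAP 4.3: "Subjects who lack any safety data for a particular vaccination will be excluded from analysis".

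**The concern.** A child who left the study after dose 1 or dose 2 cannot be observed between Visit 4 and the toddler dose. If that child stays in the denominator, the absence of data is scored as the absence of an event. Protocol 6.2 does not replace vaccinated children who withdraw, so they remain in N.

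The other two SAE intervals do not have this problem. The first starts at the dose that defines the infant population, and the third uses children who received the toddler dose. Only the middle interval has a denominator unrelated to having entered it. It is also the longest, from about 18 weeks to 12 months of age, and under protocol 8.1.4 only SAEs and newly diagnosed chronic conditions are collected in it.

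What is at stake is the accuracy of descriptive rates and their exact intervals in a study that the protocol defines as a postauthorization safety study. The error runs towards fewer events, and would differ between groups if early loss did.

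**Working it through.** **The plan's own figure.** Protocol Table 5 gives the chance of at least one event among 150 MDV subjects. Using 1 − (1 − p)^150, p = 50.0%, 0.6% and 0.2% give 100.0%, 59.45% and 25.94%, matching the stated 100.0%, 59.5% and 25.9%. The table concerns the infant series and does not settle the denominator for the later interval.

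**Does any rule remove early leavers?** The SAP 4.3 exclusion is tied to a particular vaccination. No vaccination opens the middle interval, so a child with dose 1 data who then left is not clearly excluded. SAP 5.3.2 ties its missing-reactogenicity denominator to receipt of the scheduled dose, and there is no counterpart for this interval.

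**Formula.** Let r be the children with an event in the interval, N the ever-dosed children and d the fraction of N gone before it begins.

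- Planned rate = r / N
- At-risk rate = r / [N(1 − d)]
- Planned rate = at-risk rate × (1 − d)

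**Inputs.** N = 150 per group (protocol 9.1), taking every randomized infant to be dosed. Intervals are 2-sided 95% Clopper-Pearson (SAP 5.2.1). The documents state no dropout rate and no event rate for this interval, so d and r are assumptions. The at-risk n is rounded to a whole child.

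| d (assumed) | n | 0 events: upper 95% limit | 1 event | 3 events (95% CI) |
|---|---|---|---|---|
| 0 (as planned) | 150 | 2.43% | 0.67% | 2.00% (0.41 to 5.73) |
| 5% | 142 | 2.56% | 0.70% | 2.11% (0.44 to 6.05) |
| 10% | 135 | 2.70% | 0.74% | 2.22% (0.46 to 6.36) |
| 20% | 120 | 3.03% | 0.83% | 2.50% (0.52 to 7.13) |

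**Against the precision available.** With 3 events the largest shift shown is 2.50 − 2.00 = 0.50 points. The planned interval is 5.73 − 0.41 = 5.32 points wide.

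**Between groups.** Equal loss multiplies both rates by the same factor and leaves their ratio unchanged. For an assumed 5% against 15% loss and a true 2% in each group, the reported rates would be 2% × 0.95 = 1.90% and 2% × 0.85 = 1.70%, a spurious difference of 0.20 points.

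**The case against.** Several counter-arguments have force.

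- **Scope of the quoted sentence.** It governs supplementary SAE tables. The primary SAE endpoint runs from the first dose, where an ever-dosed denominator starts follow-up at the right time. This stands.
- **Chronic conditions.** A reader might infer that the SAP explicitly divides this primary endpoint by all infants ever dosed. It does not; SAP 6.1 leaves the population open. The ever-dosed set is the natural reading because the interval ends before the toddler dose and protocol 9.4 applies one rule to all safety analyses. The alternative, the toddler safety population, would drop children who never returned for that dose, possibly because of the condition being counted. Either way the SAP should name the set.
- **Who is affected.** Protocol 6.2 keeps children who merely stop vaccination under follow-up. Only withdrawal from the study, death or loss to follow-up creates the problem. This stands and limits d.
- **Size.** The one SAE rate in the documents is 0.2%, for the infant series. If it applied here, 10% loss would turn it into 0.18%, with about 150 × 0.002 = 0.3 expected events per group. SAP 5.1 plans no hypothesis test or decision rule. A reader might infer a material bias or a distorted group comparison, but the documents give no dropout figure or imbalance to support that.
- **Existing outputs.** SAP 5.2 requires n and N with each percentage, and SAP 6.3.1 tabulates disposition, vaccinations and blood samples. A reader could approximate the at-risk number. That reduces the harm, but the published rate and interval would still rest on the larger N.
- **Protocol consistency.** Replacing the denominator of a primary endpoint departs from protocol 9.4, and major changes to primary analyses must also be reflected in a protocol amendment. Keeping the ever-dosed rate alongside meets this point.

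**Conclusion.** The concern holds for SAEs in the middle interval, where the SAP fixes an ever-dosed denominator and no other rule clearly removes children lost beforehand. For newly diagnosed chronic conditions the firm finding is narrower: the population is unnamed, and the same denominator is the likely but inferred reading.

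The relative understatement equals d. For an assumed 5% to 20%, it is at most 0.50 points with 3 events in 150, and with no events it lowers the upper limit by 0.13 to 0.60 points (2.56% − 2.43% and 3.03% − 2.43%). No test is affected. It merits correction because the error runs in one direction, one of the endpoints is primary, and disposition data already allow a better denominator.

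**What to change.** In SAP 6.1 and 6.4.1, for both chronic conditions and SAEs in this interval:

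- Use as denominator the infant safety subjects who, by disposition status, had not withdrawn, died or been lost to follow-up when the interval began, whether or not they continued vaccination. State how that start is set for a child without a Visit 4.
- Do not make inclusion depend on later safety contact. An event can prompt such contact, which would bias incidence upward.
- Beside each rate, show how many children reached the toddler dose. A denominator fixed at the start of the interval does not correct for loss within it, so that loss should be visible.
- Keep the ever-dosed rate alongside for consistency with protocol 9.4.

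The cost is one derived flag, a few SAP sentences and slightly wider confidence intervals, with no new data collection. If the at-risk rate were to replace the ever-dosed rate for the primary endpoint, the sponsor would need to decide whether a protocol amendment is required.

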#### **6.4.2. Unscheduled Visits (Unplanned Visits) for Severe Reactions**

A listing will be generated for all of the subjects with unscheduled/unplanned visits because of severe (Grade 3) reactions.

#### **6.4.3. Physical Examinations, Including Vital Signs**

Descriptive summary tables will be provided in accordance with Pfizer reporting standards.

#### **6.4.4. Nonstudy Vaccinations and Nonstudy Medications**

Nonstudy vaccinations will be summarized descriptively. Nonstudy medications are not collected in this study.

### **7. INTERIM ANALYSES**

No formal interim analysis will be conducted. However, as this is an open-label study, the sponsor may conduct unblinded reviews of the data during the course of the study for the purpose of safety assessment or to support clinical development. This includes compilation of results of the infant series before completion of the toddler dose.

